5.6.6 Laboratory, Biomarker, and Other Biological Samples

Samples for the following laboratory tests will be sent to the study site's local laboratory for analysis:

- Hematology: WBC count, RBC count, hemoglobin, hematocrit, platelet count, differential count (neutrophils, eosinophils, basophils, monocytes, lymphocytes, other cells)
- Chemistry panel (serum or plasma): sodium, potassium, magnesium, chloride, bicarbonate, glucose, BUN or urea, creatinine, total protein, albumin, phosphorus, calcium, total bilirubin, alkaline phosphatase, ALT, AST, LDH, CPK
- Coagulation: INR, aPTT, fibrinogen, D-dimer
- Thyroid function testing: thyroid-stimulating hormone, free triiodothyronine (T3) (or total T3 for sites where free T3 is not performed), free thyroxine (also known as T4)
- HIV serology
- HBV serology: HBsAg, hepatitis B surface antibody, total HBcAb. If a patient has a negative HBsAg test and a positive total HBcAb test at screening, an HBV DNA test should be performed at screening.
- HCV serology: HCV antibody and (if HCV antibody test is positive) HCV RNA. If a patient has a positive HCV antibody test at screening, an HCV RNA test must also be performed to determine if the patient has an active HCV infection.
- Pregnancy test. All women of childbearing potential will have a serum/urine pregnancy test at screening. A woman is considered to be of childbearing potential if she is postmenarcheal, has not reached a postmenopausal state (≥ 12 continuous months of amenorrhea with no identified cause other than menopause), and has not undergone surgical sterilization (removal of ovaries and/or uterus).
- Urinalysis (pH, specific gravity, glucose, protein, ketones, and blood); dipstick permitted
- *The following samples will be sent to one or several central laboratories or to the Genentech Inc. for analysis:*
- **Blood** samples for translational research on biomarkers (See Appendix 9).
- Tumor tissue samples will be collected for exploratory research on biomarkers (See Appendix 9).

- a. Fresh tumor tissue sample (or archival tissue) will be collected at baseline for determination of PD L1 expression and for exploratory research on biomarkers
 - Tissue should be collected by excisional or core needle biopsy, typically using a 21-18 gauge needle. The biopsy should include at least 5 cores, 2 FFPE and 3 fresh frozen. It should be collected within 28 days prior to initiation of protocol therapy.

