 - For archival tissue: a representative FFPE tumor specimen in a paraffin block (preferred) or at least 10 slides containing unstained, freshly cut, serial sections need to be submitted along with an associated pathology report. Tumor tissue should be of good quality based on total and viable tumor content. Samples should ideally contain a minimum of 50 viable tumor cells that preserve cellular context and tissue architecture regardless of needle gauge or retrieval method. Samples collected via resection, core-needle biopsy (at least three cores, embedded in a single paraffin block), or excisional, incisional, punch, or forceps biopsy are acceptable.
 - Considering the benefit seen with immunotherapy in MSI-H colon cancer, we will perform MSI tests on patients with small bowel and appendiceal adenocarcinoma.
- b. Tumor tissue sample will also be collected at week 4 for exploratory research on biomarkers
 - Biopsies at week 4 should be performed within 7 days before administration of C2D1 of study therapy. Samples collected via resection, core-needle biopsy (at least three cores preferred), or excisional, incisional, punch, or forceps biopsy are preferred.
- c. Tumor tissue sample will also be collected at time of progression for exploratory research on biomarkers
 - Biopsies at the time of progression should be performed within 40 days after progression or prior to the next anti-cancer therapy, whichever is sooner. Samples collected via resection, core-needle biopsy (at least three cores preferred), or excisional, incisional, punch, or forceps biopsy are preferred.
 - For cutaneous squamous cell carcinoma, where local therapy options may be considered in the future, the lesions biopsied will be documented at each time point and if possible, a sample will be collected in patients who go to surgery. The location of the sample collected at surgery will also be documented.

Blood and tissue collections will be tracked by Tissue Station. Collection requests will be placed in the system, prior collections, and updated once completed including details of the process. All samples shipped to Genentech will be tracked and documented in Tissue Station,

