5.10.3 Determination of Sample Size

The primary endpoint is best ORR (PR or CR), measured as per RECIST 1.1. Three parallel single-stage phase II trials will be conducted. A total of 60 patients will be enrolled, i.e., 20 patients in each tumor group. Considering the rareness of the disease, the patient accrual rate is approximately 1 to 2 patients per month per tumor group.

Sample size calculation

For each tumor group, we will estimate the best ORR and its exact confidence interval (CI). When the sample size is 20, and the response rate is 0.3, the two-sided 95% exact CI using the Clopper and Pearson method will be (0.119, 0.543).

For each tumor group, we will also compare its overall best response rate to the historical control based on the current literature. Let p represent the overall best response rate, we will perform independent Binomial test against $H_0: p=0.1$ for each group, with a 1-sided type I error rate of 0.05. The sample size of 20 will provide 76% power to detect an improved best ORR being 30% compared to 10%.

Analysis Plan

The primary outcome is the best ORR since the start of treatment. For each tumor group, we will estimate the best response rate and its 95% exact confidence interval using the Clopper and Pearson method. And we will assess the efficacy of the combination treatment by performing the independent binomial test comparing the best response rate versus the historical control for each tumor group. The primary efficacy analyses will include all treated patients who have received at least one dose of study treatment and have baseline tumor assessment. Patients who do not receive at least 1 dose of therapy will be replaced.

For each tumor group, median DOR and corresponding 2-sided 95% CI will be reported. The association between the best ORR and other variables will be assessed using the Fisher's exact test. Time-to-event outcomes, including progression free survival (PFS) and overall survival (OS), will be estimated using Kaplan-Meier method. The log-rank test will be performed to test the difference in time-to-event distributions between patient groups. Cox proportional hazards model may be utilized to include multiple covariates in the time-to-event analysis.

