Appendix 2 Response Evaluation Criteria in Solid Tumors (RECIST Criteria)

The RECIST criteria should be used to assess response to treatment. Only patients with measurable disease should be entered in the study. Measurable disease is defined as the presence of one lesion that can be accurately measured in at least one dimension (longest diameter to be recorded) as ≥ 2.0 cm with conventional techniques (or as ≥ 1.0 cm by spiral CT). Evaluable lesions should be followed for the assessment of response. Non-measurable lesions include bone lesions, leptomeningeal disease, ascites, pleural/pericardial effusion, lymphangitic carcinomatosis, abdominal masses that are not confirmed by CT, and cystic lesions.

All measurable lesions, up to a maximum of 5 lesions per organ and 10 lesions in total, representative of all involved organs, should be identified as target lesions and recorded and measured at baseline. A sum of the longest diameter for all target lesions will be calculated and reported as the baseline sum longest diameter. The baseline sum longest diameter will be used as the reference by which to characterize the objective tumor response.

- Complete response (CR)
Disappearance of all evidence of tumor for at least two cycles of therapy. Tumor markers must be normal.
- Partial response
At least a 30% decrease in the sum of the longest diameter of target lesions, taking as reference the baseline sum longest diameter.
- Stable disease (SD)
Neither sufficient shrinkage to qualify for partial response nor sufficient increase to qualify for progressive disease, taking as reference the smallest sum longest diameter since the treatment started.
- Progressive disease (PD)
At least a 20% increase in the sum of the longest diameter of target lesions, taking as reference the smallest sum longest diameter recorded since the beginning of treatment or the appearance of one or more new lesions.
- Clinical progressive disease
Patients, who in the opinion of the treating physician investigator have had a substantial decline in their performance status and have clinical evidence of progressive disease may be classified as having progressive disease.

**Appendix 3 National Cancer Institute Common Toxicity Criteria
for Adverse Events**

Version 4 of the NCI-CTC-AE can be obtained from:

<http://evs.nci.nih.gov/ftp1/CTCAE/About.html>

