A sum of the diameters (longest diameter for non-lymph node lesions, short axis for lymph node lesions) will be calculated for all target lesions at baseline as a measure of tumor burden. At each subsequent tumor assessment, a sum of the diameters (longest diameter for non-lymph node lesions, short axis for lymph node lesions) will be calculated for all target lesions plus measurable new lesions (up to five new lesions, with a maximum of two new lesions per organ) that have emerged after baseline. Hence, each net percentage change in tumor burden per assessment accounts for the size and growth kinetics of both old lesions and new lesions as they appear.

Measuring Lymph Nodes

If at first appearance the short axis of a new lymph node lesion is ≥ 15 mm, it will be considered a measurable new lesion and may be included in the sum of the diameters. If the new lymph node lesion is included in the sum of diameters, it will continue to be measured and included in the sum of diameters at subsequent timepoints, even if the short axis decreases to < 15 mm (or even < 10 mm). However, if it subsequently decreases to < 10 mm and all other lesions are no longer detectable or have also decreased to a short axis of < 10 mm (if lymph nodes), a response assessment of complete response may be assigned.

Lymph nodes should always have the actual short axis measurement recorded (measured in the same anatomical plane as the baseline examination), even if the node regresses to < 10 mm during the study. Thus, when lymph nodes are included in the sum of diameters, the sum may not be zero even if complete response criteria are met, since a normal lymph node is defined as having a short axis of < 10 mm.

Measuring Lesions That Become Too Small to Measure

During the study, all target lesions and up to five measurable new lesions (lymph node and non-lymph node) should have their actual measurements recorded at each subsequent evaluation, even when very small (e.g., 2 mm). However, sometimes lesions or lymph nodes become so faint on CT scan that the radiologist may not feel comfortable assigning an exact measurement and may report them as being too small to measure. When this occurs, it is important that a value be recorded on the CRF, as follows:

If it is the opinion of the radiologist that the lesion has likely disappeared, the measurement should be recorded as 0 mm.

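### Nothing keeps the week-4 research biopsy, which may be an excision or resection, away from RECIST target lesions, and no rule says how a removed target lesion counts in the primary ORR

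*Combined protocol and SAP*

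**What the plan says.** **Sampling.** Section 4.1 makes the on-treatment biopsy mandatory unless it is not clinically feasible. On timing, Section 5.6.6(b) says: "Biopsies at week 4 should be performed within 7 days before administration of C2D1 of study therapy". On method it says: "Samples collected via resection, core-needle biopsy (at least three cores preferred), or excisional, incisional, punch, or forceps biopsy are preferred". The same method sentence appears for the progression sample, but for the primary endpoint the week-4 item is the one that matters. Appendix 8 plans a core needle or excisional biopsy before and after treatment. For fresh baseline tissue, Section 5.6.6(a) says: "Tissue should be collected by excisional or core needle biopsy, typically using a 21-18 gauge needle".

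**Response assessment.** Section 5.6.5 schedules scans at baseline and every 8 weeks, read by a blinded radiologist at the imaging core. Appendix 2 selects as targets "All measurable lesions, up to a maximum of 5 lesions per organ and 10 lesions in total, representative of all involved organs". It defines PR as a fall of at least 30% in the target sum from baseline, and one measurable lesion is enough for entry. Section 5.10.3 takes best response since the start of treatment as the primary outcome and does not ask for PR to be confirmed.

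**Existing protections.** Section 5.4.1 allows palliative radiotherapy only if it does not disturb assessment of target lesions. It also delays surgery or definitive radiation in cSCC until at least two cycles have been given, and Section 5.6.5 adds that at least one tumor assessment must come first. None of these rules mentions biopsies.

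**The concern.** If a target lesion is excised between the baseline scan and the week-8 scan, the sum of diameters falls because tissue was taken out. Appendix 2 does not ask why the sum fell, so the patient can be recorded as a PR. For a removal in that interval the error runs one way, towards a false positive. There is no control arm to reveal it, and each 20-patient cohort is decided by a handful of responders. Requiring confirmation would not help, because an excised lesion stays absent. The loss also cannot be repaired at analysis, since what that lesion would have done on treatment is never observed.

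**Working it through.** **1. The plan's own figures.** Section 5.10.3 gives n = 20 per cohort, a null rate of 0.10, an alternative of 0.30, a test "with a 1-sided type I error rate of 0.05", and 76% power. With X ~ Bin(20, p):

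- P(X ≥ 4 | 0.10) = 0.1330, too large.
- P(X ≥ 5 | 0.10) = 0.0432, so success means at least 5 responders.
- P(X ≥ 5 | 0.30) = 0.7625, which reproduces the 76%.
- The Clopper-Pearson interval for 6/20 is (0.119, 0.543), as stated.

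**2. Timing.** Cycles last 28 days, so the week-4 sample falls on about Days 22 to 28. The first scheduled scan is at about Day 56, which is 28 to 34 days later. The cSCC rule on local therapy (two cycles = 56 days, plus one assessment) would not be met at the time of the biopsy.

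**3. Effect of removal on the target sum, other lesions unchanged.** With m equal target lesions, removing one changes the sum by −1/m:

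| Target lesions | Change in sum | Meets −30%? |
|---|---|---|
| 1 | −100% | yes |
| 2 | −50% | yes |
| 3 | −33% | yes |
| 4 | −25% | no |

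Unequal example: 20 + 15 + 15 = 50 mm. Removing one 15 mm lesion leaves 35 mm, and (50 − 35)/50 = 30%, exactly at the threshold. Growth can also be hidden. With two equal lesions of size d, one removed and the other growing by a fraction g, the change is [d(1 + g) − 2d]/2d. This equals −30% when g = 0.40.

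**4. Effect on the primary test at a true ORR of 10%.** The documents do not say how often this would happen, so the counts and rates below are assumptions.

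If exactly k of the 20 patients are certain to be scored PR because of removal, the chance of success is P(Bin(20 − k, 0.10) ≥ 5 − k):

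- k = 0: 0.0432
- k = 1: P(Bin(19, 0.10) ≥ 4) = 0.1150
- k = 2: P(Bin(18, 0.10) ≥ 3) = 0.2662

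If instead a share q of true non-responders is scored PR, the effective rate is 0.10 + 0.90q:

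| q (assumed) | Effective rate | P(X ≥ 5) |
|---|---|---|
| 0 | 0.1000 | 0.043 |
| 2.5% | 0.1225 | 0.089 |
| 5% | 0.1450 | 0.153 |
| 10% | 0.1900 | 0.327 |

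**5. Baseline sample.** A fresh baseline biopsy and the baseline scan each fall within 28 days before treatment, and no order is set (Section 5.6.6(a); Appendix 1, footnote h). If the scan comes first and a target is then excised, the effect is the same as in step 3. If the biopsy comes first, the lesion is not in the baseline sum and there is no effect.

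**The case against.** The best defence is that the method sentence lists acceptable specimen types and does not rank surgery above needles. The archival-tissue bullet in Section 5.6.6 uses almost the same list. The practical text points to cores: needle gauges are given, and Appendix 8 lets the radiologist who performs the procedure decide the number of cores. The general criterion asks for metastatic or unresectable disease, and appendiceal patients must not be candidates for curative surgery, so a research resection at week 4 is unlikely in the two gastrointestinal cohorts. With four or more equal targets, removing one does not reach 30%. A new lesion, or enough growth elsewhere, also prevents a PR. This all stands, and it limits the point to excision or resection, chiefly in cSCC and in patients with one to three targets.

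Three further readings are tempting but not supported:

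- A reader might infer that an excised lesion must be scored as zero, because Appendix 4 says: "If it is the opinion of the radiologist that the lesion has likely disappeared, the measurement should be recorded as 0 mm". That sentence concerns lesions that become too faint to measure and sits in the immune-modified criteria. The same appendix says that measuring only some of the targets usually makes the timepoint not evaluable, which fits a removed lesion at least as well. Appendix 2, which Section 5.6.5 cites for RECIST v1.1 reads, contains neither rule.
- A reader might infer that nobody records what was biopsied outside cSCC. The explicit rule to document the lesion is in the cSCC bullet, but Section 5.6.6 also tracks every collection in Tissue Station with details of the process, and it refers to a laboratory manual that is not among the documents. What is missing is a step that passes lesion identity to the imaging core.
- A reader might infer that the baseline sample is always at risk. Archival tissue is accepted in Section 5.6.6(a), and footnotes m and n of Appendix 1 differ on when a fresh biopsy is needed.

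**Conclusion.** The gap is real and should be fixed. Followed as written, the plan allows surgically removed tumor to count as a response in the primary ORR, and no stated rule prevents it. The protections for palliative radiotherapy and for cSCC local therapy show that the hazard was recognised, but they do not extend to biopsies.

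The size of the bias cannot be estimated from the documents. The rise from 4.3% to 11.5% or 26.6% assumes one or two patients certain to be scored PR because of removal, with the other patients responding at 10%. A reader might take these figures as the trial's actual type I error, or conclude that target lesions will routinely be excised. Neither follows: most samples are likely to be needle cores, which barely change a diameter. The case for acting is that the primary endpoint is exposed for the sake of an exploratory sample, and that the remedy is cheap and works only if it is set in advance.

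**What to change.** - **Sections 5.6.6 and Appendix 8.** Take on-treatment research samples, and any fresh baseline sample obtained after the baseline scan, from a non-target lesion where one exists; otherwise use core or punch sampling only. Do not excise or resect a target lesion for research before the first post-baseline scan.
- **Appendix 2.** State that removal of a target lesion cannot by itself create a PR or CR in the primary ORR, and prespecify one convention. For example, a patient whose response depends on the removed lesion counts as a non-responder. Dependence can be checked by recomputing the sum with that lesion's last measured diameter carried forward.
- **Data flow.** Record the biopsied lesion and the method in all three cohorts, and send this to the imaging core before the read.

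The cost is a few sentences, one extra eCRF field and slightly less tissue in some patients. With no removal-driven responses, the design keeps its rule of 5/20, its exact type I error of 0.043 and its power of 0.762, with no change in sample size.

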5.6.7 Assessments during Screening and Treatment

The following are recommended evaluations (Please refer to the current atezolizumab and cobimetinib Investigator's Brochures for guidance to the investigator on the management of safety concerns associated with atezolizumab and cobimetinib therapy):

- Physical examination: Routine physical is needed.
- Monitor complete blood count (CBC), chemistries, and liver function test, etc. per institutional guidelines
- Ophthalmologic examination – Screening, C2D1, then q 3 cycles and as clinically indicated
 - a. Ophthalmologic examinations will include visual acuity testing, intraocular pressure measurements by tonometry, slit-lamp ophthalmoscopy, indirect ophthalmoscopy, and spectral domain optical coherence tomography (OCT). If spectral domain OCT is not available, time-domain OCT may be performed instead. Ophthalmologic examination must be performed by a qualified ophthalmologist.
- LVEF – Evaluate left ventricular function using echocardiogram (ECHO) or MUGA. All patients will undergo evaluation of left ventricular dysfunction by ECHO at screening. Further, evaluation of LVEF by ECHO must be performed at the following timepoints: Cycle 2, Day 1 ± 1 week; Day 1 of Cycles 5, 8, and 11 (every 3 treatment cycles) ± 2 weeks; Day 1 of Cycles 15+ (every 4 treatment cycles) ± 2 weeks.
- Unscheduled Assessments

- A clinic visit should be scheduled any time there is a safety issue or any unscheduled assessments need to be performed as well as tumor assessments as clinically indicated.

5.6.8 Follow-Up Assessments

Please see Appendix 1 for the schedule of assessments performed during the study.

- **For progression-free survival follow-up**

Patients who discontinue treatment for reasons other than disease progression (e.g., toxicity) will continue scheduled tumor assessments until disease progression, withdrawal of consent, study termination by PI, or death, whichever occurs first.

- **For survival follow-up**

Patients who discontinue study treatment for reasons other than withdrawal of consent will be followed for survival and subsequent anti-cancer therapies approximately every 3 months until death, loss to follow-up, withdrawal of consent, or study termination by PI. During this period, documentation of anti-cancer therapies should include administration start and stop dates.

Required follow-up information will be collected via telephone calls and/or clinic visits every 3 months until death, withdrawal of consent, the patient is lost to follow-up, or study termination by the Sponsor, whichever occurs first.

5.7 DISCONTINUATION OF PROTOCOL-SPECIFIED THERAPY

Protocol-specified therapy may be discontinued for any of the following reasons:

- Progressive disease (See section 5.3.4 for treatment beyond RECIST progression).
- Unacceptable toxicity
- Patient election to discontinue therapy (for any reason)
- Physician's judgment

5.8 PATIENT DISCONTINUATION

Patients have the right to voluntarily withdraw from the study at any time for any reason. In addition, the investigator has the right to withdraw a patient from the study at any time. Reasons for withdrawal from the study may include, but are not limited to, the following:

- Patient withdrawal of consent at any time
- Any medical condition that the investigator determines may jeopardize the patient's safety if he or she continues in the study
- Investigator determines it is in the best interest of the patient
- Patient non-compliance

Every effort should be made to obtain information on patients who withdraw from the study. The primary reason for withdrawal from the study should be documented on the appropriate Case Report Form. However, patients will not be followed for any reason after consent has been withdrawn. Patients who withdraw from the study will be replaced.

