5.10 STATISTICAL METHODS

5.10.1 Analysis of the Conduct of the Study

This is a single-arm, Phase IIA, single-center, open-label study designed to evaluate the safety and efficacy of cobimetinib plus atezolizumab in approximately 20 patients per cohort of advanced rare cancers.

The efficacy analyses of OS, PFS, and ORR will be performed on all treated patients. DOR will be assessed in patients who have an objective response. The safety population will include all patients who received any amount of study drug. Patients who are enrolled into the study but do not receive any amount of study drug will not be included in the safety population.

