9.3 ADMINISTRATIVE STRUCTURE

This trial will be supported via the rare disease strategic alliance between The University of Texas MD Anderson Cancer Center and Genentech. The University of Texas MD Anderson Cancer Center will be the sole site, responsible for enrolling approximately 60 total patients.

The MD Anderson Cancer Center IND office will provide oversight of safety (see Section 6.0).

After written informed consent has been obtained, the study team will generate a unique study identification number for the patient.

Patient data will be recorded via an EDC system with use of eCRFs.

Central laboratories, including those at Genentech/Roche/Roche collaborators and at The University of Texas MD Anderson Cancer Center, will be used for PD-L1 expression status determination and will provide kits for pharmacogenomics, tissue, whole blood, serum, and plasma sample analyses to be conducted at central laboratories or Genentech Inc.

Treatment decisions will be made on the basis of the local reading of ECGs obtained during the study.

Imaging data will be retained at The University of Texas MD Anderson Cancer Center.

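### Does replacing every patient who withdraws, including those already dosed, undermine the 76% power stated for 20 patients per cohort?

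*Combined protocol and SAP*

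**What the plan says.** Section 5.8 (Patient Discontinuation) opens with "Patients have the right to voluntarily withdraw from the study at any time for any reason", lets the investigator withdraw a patient too, and ends with "Patients who withdraw from the study will be replaced". Nothing there depends on whether the patient has been dosed.

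Section 5.10.3 (Determination of Sample Size, under Analysis Plan) has its own replacement sentence: "Patients who do not receive at least 1 dose of therapy will be replaced". Just before it stands the analysis set: "The primary efficacy analyses will include all treated patients who have received at least one dose of study treatment and have baseline tumor assessment". Section 5.10.1 puts it more briefly: "The efficacy analyses of OS, PFS, and ORR will be performed on all treated patients".

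The power statement, also in 5.10.3, is "The sample size of 20 will provide 76% power to detect an improved best ORR being 30% compared to 10"%. It belongs to a binomial test against a 10% response rate in each tumor group, one-sided at 0.05, and the same section sets 20 patients per group and 60 in all. Elsewhere the numbers are looser: "approximately 20 patients per cohort of advanced rare cancers" in section 5.10.1 and "responsible for enrolling approximately 60 total patients" in section 9.3.

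**The concern.** The two sections seem to replace different patients. Staff working from 5.8 would replace a patient who withdraws after several cycles; a statistician working from 5.10.3 might expect replacement only before the first dose. Because the primary analysis retains all treated patients with a baseline scan, a replaced dosed withdrawal is counted and so is the substitute. The cohort then exceeds 20, no maximum is stated, and the only power figure is for exactly 20.

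Power is what is at stake. With so few patients the exact test moves in steps, and 20 sits just before a step. One extra patient raises the required number of responders from 5 to 6 and lowers the chance of declaring activity. There is a second hazard: an analyst who kept the cut-off of 5 in a larger cohort would exceed the planned type I error.

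**Working it through.** **Inputs from section 5.10.3.** Null rate 0.10, alternative 0.30, one-sided level 0.05, n = 20 per cohort. The documents give no withdrawal rate, so every rate below is an assumption.

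**Formulas.** The cut-off c(n) is the smallest r with P(X ≥ r | n, 0.10) ≤ 0.05. Power is P(X ≥ c(n) | n, 0.30), with X binomial.

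**The plan's own figure.** At n = 20, c = 5: actual level 0.0432, power 0.7625. The stated 76% is reproduced.

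**Larger cohorts, every patient responding at 30%.**

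| n | c(n) | actual level | power |
|---|---|---|---|
| 20 | 5 | 0.0432 | 76.2% |
| 21 | 6 | 0.0144 | 63.7% |
| 22 | 6 | 0.0182 | 68.7% |
| 23 | 6 | 0.0226 | 73.1% |
| 24 | 6 | 0.0277 | 77.1% |
| 27 | 6 | 0.0471 | 86.4% |
| 28 | 7 | 0.0179 | 78.0% |

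From 20 to 21 patients power falls by 76.2 − 63.7 = 12.5 points, while the actual level falls from 0.0432 to 0.0144, a third of what it was. The fall reflects a stricter test, not lost information. Keeping c = 5 would give levels of 0.0522, 0.0621 and 0.0731 at n = 21, 22 and 23; that would be a misapplication of the planned 0.05 test, since the plan fixes the level and not a cut-off.

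**Averaged over an assumed withdrawal rate w.** Suppose replacement continues until 20 dosed patients have not withdrawn. The number replaced, K, is then negative binomial (20 non-withdrawals, probability 1 − w each). If everyone responds at 30%, expected power is the sum over K of P(K) × P(X ≥ c(20+K) | 20+K, 0.30):

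| w | expected power | expected actual level |
|---|---|---|
| 5% | 70.2% | 0.0264 |
| 10% | 71.3% | 0.0237 |
| 15% | 74.7% | 0.0262 |
| 20% | 78.1% | 0.0292 |

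The comparison is 76.2% without replacement. The shortfall vanishes at w of about 17% and becomes a gain beyond that.

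**If dosed withdrawals never respond.** This assumption is harsher and often closer to practice. With k such withdrawals:

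- Replaced: P(X ≥ 6 | 20, 0.30) = 58.4% for every k from 1 to 7.
- Not replaced: P(X ≥ 5 | 20 − k, 0.30), as below.

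| k | replaced | not replaced |
|---|---|---|
| 1 | 58.4% | 71.8% |
| 2 | 58.4% | 66.7% |
| 3 | 58.4% | 61.1% |
| 4 | 58.4% | 55.0% |
| 5 | 58.4% | 48.5% |
| 6 | 58.4% | 41.6% |
| 7 | 58.4% | 34.6% |

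Averaged over w, replaced against not replaced: 64.8% against 71.5% at 5%, 60.5% against 66.2% at 10%, 58.3% against 60.5% at 15%, 55.6% against 54.4% at 20%. The order switches at about 18%.

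**The two sections side by side.** Section 5.10.3 says undosed patients are replaced; it does not say that nobody else is. Section 5.8 adds those who withdraw. Both can be carried out together, and the analysis set is the same whichever sentence triggered the replacement. Stopping therapy alone (section 5.7) carries no replacement rule, and section 5.6.8 keeps patients who stop for reasons other than progression on scheduled scans. The event that enlarges a cohort is therefore withdrawal from the study, which is narrower than stopping treatment.

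**The case for a change.** The strongest case for a change is that it costs two sentences, and that the dip lies where it is most likely to be met. Under the negative binomial model above, the chance that a cohort has one to three replacements is 62% at an assumed 5% withdrawal rate and 69% at 10%. Extra patients usually help; here the first three hurt. The plan neither caps the cohort nor gives power beyond 20. The listed toxicity boundaries in section 5.10.5 also end at 60 treated patients. A single stated rule would remove the ambiguity and guard against using the 20-patient cut-off in a larger cohort.

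Most of this is accurate, and as drafting it would be tidier. It does not carry the step to a change in the plan. Limiting replacement to undosed patients does not protect the 76%: if withdrawals are non-responders, that rule falls short from the first withdrawal and is the weaker rule from the fourth. Quoting a maximum cohort size with its power leaves the dip at 21 to 23 where it is, and an attractive figure such as 86.4% at 27 is a local peak, followed by 78.0% at 28. The cut-off slip is not in the plan, which asks for a test at level 0.05. For toxicity, section 5.10.5 gives the posterior criterion from which the boundaries come, so a boundary beyond 60 follows from the same rule.

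**Conclusion.** No change follows. The difference in wording is real, but the two replacement sentences are compatible, and an overrun of a few patients fits numbers that sections 5.10.1 and 9.3 call approximate. Every dosed patient with a baseline scan stays in the analysis, so replacement does not select who is counted, and the exact test at the actual n holds type I error below 5% (0.0144 to 0.0471 for n = 21 to 27).

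What remains is a conditional effect on power. With all patients responding at 30%, it is a loss of 12.5 points at one replacement, 7.5 at two (76.2 − 68.7) and 3.1 at three (76.2 − 73.1), and a gain of 0.9 at four (77.1 − 76.2). Averaged over assumed withdrawal rates it is a loss of 6.0 points at 5% (76.2 − 70.2), 4.9 at 10% (76.2 − 71.3) and 1.5 at 15% (76.2 − 74.7), changing sign at about 17%. If withdrawals are non-responders, the comparison with not replacing changes sign at about 18%. Since the documents give no rate, neither rule is clearly better, and the choice is a fair trade-off in a study that section 5.10.4 describes as hypothesis-generating. An analyst who takes the cut-off at the number actually analysed, and reports that number, fills the gap.
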